6.1 Potential Study Risks

The potential risks to participants, their likelihood and seriousness, and strategies to mitigate risks are described below. Participants can choose, as an alternative, to not enroll in this study. Overall, there is minimal risk for serious adverse reactions as a consequence of enrolling in this study. Adverse reactions/AEs will be collected, assessed, and reported as per the study protocol (see section 8: Safety and Adverse Events), federal law, and University of Pennsylvania regulations.

Withdrawal Syndrome: Many individuals who abstain from smoking exhibit a pattern of symptoms related to withdrawal from tobacco use. These symptoms include: anger, irritability, frustration, anxiousness or nervousness, depressed mood or sadness, cravings for nicotine, difficulty concentrating, appetite change and weight gain, insomnia or other sleep problems, restlessness, impatience, constipation, dizziness, coughing, nightmares, nausea, sore throat, headache, muscular pain, or fatigue. Eliminating the risk for these would not be possible, although in most cases these events are short-lived and have low intensity. The study personnel will be trained to recognize these symptoms and educate the participants about them (e.g., duration and methods for reducing them).

Food Allergies: Participants will be provided with nutritional shakes and potato chips or milk chocolate as part of their participation in this research trial. The risk of a participant experiencing an allergic reaction to any of the ingredients in these commercially available food products will be mitigated by prospectively excluding those with the applicable food allergies. In addition, the research staff will reconfirm that the participant doesn't have any of the applicable food allergies prior to distribution of the aforementioned food products at the Baseline Visit.

Psychological Distress: Participants may experience emotional distress during smoking cessation counseling and assessments from discussing feelings and attitudes about smoking or from learning about the risks from smoking. These events happen very rarely and in almost all cases are short-lived and of low intensity, lasting for 1-2 weeks. Study personnel will be alerted to expect this from a small number of subjects and will be trained to make referrals for mental health services as needed. Personnel will be trained to query for adverse emotional reactions during counseling and assessments and will be trained to deal with such reactions and to provide additional referrals if needed.

Urine Sample Collection: Participants may experience mild discomfort from providing urine samples. All samples will be collected by trained member of the research staff.

Email Communications: In this research study participants may prefer to receive appointment reminders via email or submit questions related to participation via email. Email is not a secure means of communication. Email messages travel across the Internet, passing through multiple computers before reaching their final destination. It is not possible to know whether an email a participant sends will be viewed along the way. Additionally, if sent messages are not deleted, an email provider may have an archive of everything that is sent. If someone gets access to an email account (for example, a participant's family member), they could see archived messages.

CONFIDENTIAL

This material is the property of the University of Pennsylvania. Do not disclose or use except as authorized in writing by the study sponsor

There are many other ways in which emails are not secure—these are only selected examples. To manage this risk, the informed consent form will include specific language to educate research participants on the privacy risks involved in email communications. Participants will also be explicitly instructed to only use email communications for routine matters and never for personal or confidential messages or questions.

fMRI: The known MRI-related risks associated with this study are minimal. All sequences and RF coils will be approved by the Center for Magnetic Resonance Imaging and Spectroscopy (CAMRIS) prior to utilization. Because of the strong magnetic field, people with pacemakers, certain metallic implants, or metal in the eye cannot participate in this study. These exclusions will be reviewed carefully with the study staff prior to scanning.

The greatest risk with MRI is a metallic object flying through the air toward the magnet and hitting the participant. To reduce this risk, we require that all people involved with the study remove all metal from their clothing and all metal objects from their pockets. No metal objects are allowed in the magnet room at any time. In addition, once the participant is in the magnet, the door to the room will be closed so that no one inadvertently walks into the magnetic field. Although there are no known risks of MRI on pregnant women or a fetus, there is a possibility of yet undiscovered pregnancy related risks. Since there is no direct benefit from participating in this protocol for a pregnant woman, women of childbearing potential will be supplied with a simple, CLIA-waived urine pregnancy screen to self-administer at each scan visit, and will be told that pregnant women may not participate in the study. They will then be instructed to administer the pregnancy test independently and will inform study staff if they would like to continue participation after they have administered the pregnancy screen. Participants will be informed that there is no penalty for discontinuing participation at this point in the visit and that they will still be provided their preferred travel coverage for the visit.

There is no known health risk associated with exposure to magnetic fields during an MRI. There are minimal risks from the loud noise associated with the MRI scanner and from the discomfort of lying on a hard surface. Participants will be provided with protective earplugs as necessary and every attempt will be made to ensure comfort with blankets, etc. during the scan.

The levels of energy used to make magnetic resonance measurements are far less than are used in a single X-ray, and many patients have been safely studied using magnetic resonance techniques. However, some people become uncomfortable or claustrophobic while inside the magnet. If participants become uncomfortable, they may withdraw immediately from the fMRI portion of the study. During some of the MRI scans, participants have occasionally reported “tingling” or “twitching” sensations in their arms or legs, especially when their hands are clasped together. To prevent this, all participants will be instructed to keep arms and legs apart.

The imaging component of this study is part of a research protocol, and is not intended to provide a comprehensive clinical fMRI examination of the brain. In the event that a significant brain abnormality is observed while processing subject brain images for the research study, the images will be reviewed by the radiologist affiliated with this protocol in conjunction with the Study Physician. There will be no charge to the subject for this examination of their images. A report will be filed in the subject's chart at the Center. The subject will be contacted and Center staff will arrange for the radiologist's report and structural images to be sent to the subject and/or their physician. Subjects will also be offered a consult with the Study Physician and/or radiologist if appropriate. These possible finding(s) may or may not be significant and may lead to anxiety about the subject's condition and to further work-up by the subject's physician.

CONFIDENTIAL

This material is the property of the University of Pennsylvania. Do not disclose or use except as authorized in writing by the study sponsor

Confidentiality and Loss of Privacy: See section 8.6.1 and 8.6.2 for methods in which Confidentiality and Subject Privacy/Protected Health Information will be secured and maintained.

6.2 Potential Study Benefits

Participants who enroll in this trial will benefit from the knowledge that they are contributing in an important way to potentially furthering scientific knowledge concerning ways to improve treatment for smokers, and prevent PCWG. Weight gain can precipitate smoking relapse and contribute to other health issues.

6.3 Risk/Benefit Assessment

There is minimal risk for serious adverse events by enrolling in this research study. The procedures used in this study have been shown to be relatively safe. Research staff will monitor subjects closely during their participation. Thus, the risk to benefit ratio for this project is perceived to be low and justifies its implementation.

7 Safety and Adverse Events

7.1 Definitions

Unanticipated Problems Involving Risk to Subjects or Others:

Any incident, experience, or outcome that meets all of the following criteria will be considered an unanticipated problem in the current study:

- Unexpected in nature, severity, or frequency (i.e. not described in study-related documents such as the IRB-approved protocol or consent form, FDA approved labeling, etc)
- Related or possibly related to participation in the research (i.e. possibly related means there is a reasonable possibility that the incident, experience, or outcome may have been caused by the procedures involved in the research)
- Suggests that the research places subjects or others at greater risk of harm (including physical, psychological, economic, or social harm).

Adverse Event:

An **adverse event** (AE) is a subcategory of the broader category of “Unanticipated Problems Posing Risk to Participants or Others” and is defined as any symptom, sign, illness or experience that develops or worsens in severity during the course of the study. Intercurrent illnesses or injuries should be regarded as adverse events. Abnormal results of diagnostic procedures are considered to be adverse events if the abnormality:

- results in study withdrawal
- is associated with a serious adverse event
- is associated with clinical signs or symptoms
- leads to additional treatment or to further diagnostic tests
- is considered by the investigator to be of clinical significance

Any event that could be characterized by the definitions above is an AE **whether or not considered related to the study**.

Serious Adverse Event:

Adverse events are classified as serious or non-serious. A **serious adverse event (SAE)** is any AE that is:

- fatal
- life-threatening
- requires or prolongs hospital stay

CONFIDENTIAL

This material is the property of the University of Pennsylvania. Do not disclose or use except as authorized in writing by the study sponsor

- results in persistent or significant disability or incapacity
- a congenital anomaly or birth defect
- an important medical event

Important medical events are those that may not be immediately life threatening, but based upon appropriate medical judgment may jeopardize the subject, and may require intervention to prevent one of the other serious outcomes noted above. For example, drug overdose or abuse, a seizure that did not result in in-patient hospitalization, or intensive treatment of bronchospasm in an emergency department would typically be considered serious. All adverse events that do not meet any of the criteria for serious will be regarded as ***non-serious adverse events***.

Adverse Event Reporting Period:

The study period during which AEs/SAEs will be reported is from the initiation of any study procedures until the end of the study. Any event(s) that the subject, or the subject's personal physician, believes might reasonably be related to participation in the study after the final time point will be assessed and reported as appropriate.

Preexisting Condition:

A preexisting condition is one that is present at the start of the study. A preexisting condition should be recorded as an adverse event if the frequency, intensity, or the character of the condition worsens during the study period.

Post-study Adverse Event:

All unresolved adverse events should be followed by the investigator until the events are resolved, the subject is lost to follow-up, or the adverse event is otherwise explained. At the last scheduled visit, the investigator should instruct each subject to report any subsequent event(s) that the subject, or the subject's personal physician, believes might reasonably be related to participation in this study.

Hospitalization, Prolonged Hospitalization, or Surgery:

Any AE that results in hospitalization or prolonged hospitalization should be documented and reported as a SAE unless specifically instructed otherwise in this protocol. Any condition responsible for surgery should be documented as an AE if the condition meets the criteria for an AE.

Neither the condition, hospitalization, prolonged hospitalization, nor surgery are reported as an adverse event in the following circumstances:

- Hospitalization or prolonged hospitalization for diagnostic or elective surgical procedures for a preexisting condition. Surgery should ***not*** be reported as an outcome of an adverse event if the purpose of the surgery was elective or diagnostic and the outcome was uneventful.
- Hospitalization or prolonged hospitalization required to allow efficacy measurement for the study.
- Hospitalization or prolonged hospitalization for therapy of the target disease of the study, unless it is a worsening or increase in frequency of hospital admissions as judged by the clinical investigator.

7.2 Collection and Recording of Adverse Events

7.2.1 AE Collection Methods

Adverse Events and SAEs will be collected by spontaneous self-report.

CONFIDENTIAL

This material is the property of the University of Pennsylvania. Do not disclose or use except as authorized in writing by the study sponsor

Research staff are trained to inquire (time of onset, nature of issue reported, possible relation to study, review of previously reported side effects or concerns, concomitant medications, severity/intensity, etc.) about any notable side effects or medical concern reported by participants. Side effects will be rated by participants utilizing the following severity scale: 0 (None=No Concerns), 1 (Mild=Side Effect or event does not interfere with usual daily activities), 2 (Moderate= Side effect does interfere with some activities), and 3 (Severe=No normal activities are possible). Any severe (or a pattern of modern) side effects or notable medical concerns will be reported to the Project Manager, Study Physician, and Principal Investigator to determine a course of action and relationship (causality) to the study procedures. This consultation, including all relevant information, will be documented via email. The clinical course of each event will be followed until resolution, stabilization, or until it has been determined that the study treatment or participation is not the cause.

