5.2.4 Mandatory Abstinence Period for Smoking Group (~days 1-3 or 29-31)

Participants will be randomized with respect to the order of the study periods; one-half of participants will have their mandatory abstinence period on days 1-4 and one-half will have this period on days 29-32. On the evening prior to the mandatory abstinence period, participants will receive a 20-minute structured telephone counseling session from a trained smoking cessation counselor to prepare for the upcoming 4-day abstinence period. Quit strategies include identifying triggers and alternative behaviors to smoking, deep breathing, and stimulus control methods. The abstinence periods will be framed as "practice quit attempts" unaided by nicotine replacement therapy or other medication.

On study days 1-3 (period 1) and 29-31 (period 2), participants will come to the Center and complete measures that may include a CO reading, breath alcohol test (BrAC), and questionnaires (smoking behavior, urges, mood, withdrawal, eating). Please see measures

CONFIDENTIAL

This material is the property of the University of Pennsylvania. Do not disclose or use except as authorized in writing by the study sponsor

table for specific time points. To verify smoking abstinence participants must have a CO reading of <10ppm or >50% reduction from their intake CO value on day 1 (or 29) and a CO reading of <5ppm on days 2, 3, or 4 (or 30, 31 & 32). Participants that do not meet CO criteria, have a BrAC greater than 0.000, or a positive urine drug screen will be withdrawn from the study, unless the Principal Investigator permits the participant to reschedule the visit to a later date.

Day 1/Day 29 Back-up Scheduling: Some participants may choose to be scheduled as a back-up for another participant's Day 1 or Day 29 visit. This is done to ensure that this protocol is efficiently using the time that is reserved on the fMRI scanner days at Days 4 and 32. Participants who are scheduled as a back-up should prepare for their back-up Day1/Day 29 in the same way that they would prepare for a primary visit. On the day of the back-up, participants should arrive at the Center in the smoking state that they have been assigned to for their respective Day 1/Day 29. Upon arrival participants will go through the same visit check-in to verify eligibility for the visit.

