5.2.7 Washout Period for Smoking Group (~days 5-28)

Between study periods there is a "washout period" (days 5-28) when participants will smoke as usual. No study visits will occur during this time.

5.2.8 fMRI Scan Visits 1 & 2 (~days 4 and 32)

Prior to each scan, participants will be instructed to fast overnight (beginning at ~10pm) until after the completion of their fMRI scanning visit the following day. The fast period will include a Boost® Nutritional Drink (Vanilla) that will be provided during the scanning visit to standardize prior food intake and remove deprivation to increase sensitivity to changes in food reward. Since participants are asked to fast overnight, all scanning sessions will be scheduled to occur in the morning. However, a scan may be completed in the afternoon at the discretion of the Principal Investigator due to extenuating circumstances. Additionally, participants will be instructed not to consume caffeine for 4 hours prior to the beginning of the visit in order standardize satiety. Including the 1-hour fMRI scan, scanning visits are expected to last ~4 hours in duration. If a scanner hardware/software malfunction occurs and data is unable to be collected, an fMRI scan(s) may be rescheduled at the discretion of the Principal Investigator.

CONFIDENTIAL

This material is the property of the University of Pennsylvania. Do not disclose or use except as authorized in writing by the study sponsor

At both scanning visits participants will:

1. Complete a urine drug screen (at least 30ml [two tablespoons] of urine). The urine drug screen will assess the use of any study-prohibited medications/recreational drugs (See Key Exclusionary Criteria; Alcohol/Drugs). Participants who test positive for any study-prohibited medications/recreational drugs will be deemed ineligible for the study at the discretion of the Principal Investigator.
2. Self-administer a CLIA-waived urine pregnancy test (female participants only). Participants who believe that they may be pregnant are instructed to discontinue participation in the study at this time.
3. Perform a BrAC assessment to control for alcohol consumption.
 - Participants with a BrAC greater than 0.000 will be ineligible to complete the study unless the Principal Investigator permits the participant to reschedule the neuroimaging scan to another day.
4. Perform a CO breath assessment

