- Related to the research study; AND
- When other participants are believed to be at an increased risk of harm

Must be reported to the IRB within 3 days from the time the investigator becomes aware of the death.

Other Reportable events:

The following events are also reportable to the Penn IRB:

- Any adverse experience that, even without detailed analysis, represents a serious unexpected adverse event that is rare in the absence of drug exposure (such as agranulocytosis, hepatic necrosis, Stevens-Johnson syndrome).
- Any adverse event that would modify the protocol or informed consent form, or would prompt other action by the IRB to assure protection of human subjects.
- Information that indicates a change to the risks or potential benefits of the research, in terms of severity or frequency. For example:
 - An interim analysis indicates that participants have a lower rate of response to treatment than initially expected.
 - Safety monitoring indicates that a particular side effect is more severe, or more frequent than initially expected.
 - A paper is published from another study that shows that an arm of your research study is of no therapeutic value.

CONFIDENTIAL

This material is the property of the University of Pennsylvania. Do not disclose or use except as authorized in writing by the study sponsor

- Change in FDA safety labeling or withdrawal from marketing of a drug, device, or biologic used in a research protocol.
- Breach of confidentiality
- Change to the protocol taken without prior IRB review to eliminate apparent immediate hazard to a research participant.
- Incarceration of a participant when the research was not previously approved under Subpart C and the investigator believes it is in the best interest of the subject to remain on the study.
- Complaint of a participant when the complaint indicates unexpected risks or the complaint cannot be resolved by the research team.
- Protocol violation (meaning an accidental or unintentional deviation from the IRB approved protocol) that in the opinion of the investigator placed one or more participants at increased risk, or affects the rights or welfare of subjects.

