9.3 Monitoring Activities

9.3.1 AE/SAE Monitoring

Monitoring and management of AEs/SAEs will be conducted in real-time by the Principal Investigator, Study Physician, and the research team at regular time points as per the methods and procedures detailed in section 8: Safety and Adverse Events.

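### Adverse events are collected by spontaneous self-report and no visit schedules a general AE question, so non-serious events are likely to be under-captured

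*Combined protocol and SAP*

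**What the plan says.** Section 7.2.1 of the combined protocol and SAP names a single collection method: "Adverse Events and SAEs will be collected by spontaneous self-report". Staff are trained to inquire "about any notable side effects or medical concern reported by participants", so their questions begin once the participant has raised something. Participants then rate side effects from 0 (none) to 3 (severe).

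Section 7.1 defines an AE broadly, as "any symptom, sign, illness or experience that develops or worsens in severity during the course of the study", whether or not it is thought related to the study. The reporting period runs from the first study procedure to the end of the study.

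Other sections touch on the same task:

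- Section 6.1, under psychological distress: "Personnel will be trained to query for adverse emotional reactions during counseling and assessments".
- Section 7.2.2 lists an SEC form among the case report forms for AEs, to be used when applicable. It does not expand the acronym or give a schedule.
- Section 9.3.1 says that AE/SAE monitoring "will be conducted in real-time by the Principal Investigator, Study Physician, and the research team at regular time points". It points to section 8 for the methods, but the AE section is number 7, and that section lists no time points.
- Section 7.3.1 gives, as one example of information reportable to the IRB: "Safety monitoring indicates that a particular side effect is more severe, or more frequent than initially expected". No expected rate or threshold is stated.

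**The concern.** The definition is wide and the stated method is narrow. A participant has little reason to know that a cold, a minor injury or a stomach upset counts as an AE, and nobody is scheduled to ask. What reaches the log therefore depends on what participants choose to mention.

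The sections on safety also leave staff unsure whether to ask. One describes active querying, another names a form without saying when it is used, and a third refers to regular time points that are not set out. At stake is the completeness of the non-serious AE record, and with it the chance of noticing that something happens more often than expected.

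**Working it through.** The documents give no AE rate, safety threshold or AE-based sample size, so there is no stated figure to reproduce. The check has three parts: the opportunities to ask, what is already asked, and an illustration of the loss under assumptions.

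**1. Opportunities to ask.** Section 5.2.4 says "On study days 1-3 (period 1) and 29-31 (period 2), participants will come to the Center and complete measures", and Section 5.2.5 applies the same visits to the smoking-as-usual period. Adding Intake, Baseline and the two scan visits:

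- Smokers: 2 + 6 + 2 = 10 staffed visits.
- Non-smokers (one period only): 2 + 3 + 1 = 6.

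Section 5.2.10 adds a 1-month follow-up for smokers. None of the procedure lists for these contacts contains a general AE question, and Table 2 has no AE row.

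**2. What is already asked.**

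| Source | Content | Said to feed the AE log? |
|---|---|---|
| MNWS (Section 5.3.2, Table 2) | 15 withdrawal symptoms, 1-week look-back; carries the smokers-only mark in Table 2 | No |
| PANAS (same places) | Positive and negative mood, 1-week look-back | No |
| Query in Section 6.1 | Emotional reactions; linked to referral | No |
| SEC form (Section 7.2.2) | Content and timing not described | A documentation form, used when applicable |

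The first three do not cover illness, injury, scan-related effects or food reactions. Section 6.1 itself lists food allergy and MRI sensations among the risks. The 30 non-smokers share those two exposures.

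Days 5-28 are 24 days without a visit (Section 5.2.7). For the half of smokers who abstain first, this window follows abstinence. A 1-week look-back on day 29 reaches only to about day 22, so even the MNWS leaves days 5-21 uncovered.

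**3. Illustration of the loss.** All rates here are assumptions. Let n = 80 completing smokers, p0 be the expected proportion with an event, 2 × p0 the true proportion, and c the fraction of events captured. Let r be the smallest count with P(Bin(80, p0) ≥ r) ≤ 0.05. The chance of flagging is P(Bin(80, 2 × p0 × c) ≥ r).

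If the expected rate comes from full capture:

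| p0 | r | c = 100% | c = 75% | c = 50% |
|---|---|---|---|---|
| 5% | 8 | 55% | 25% | 5% |
| 10% | 14 | 75% | 31% | 3% |
| 20% | 23 | 99% | 64% | 4% |

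If the expected rate was itself obtained by spontaneous report, r is set from Bin(80, p0 × c):

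| p0 | c = 100% | c = 75% | c = 50% |
|---|---|---|---|
| 5% | 55% | 39% | 21% |
| 10% | 75% | 67% | 55% |
| 20% | 99% | 95% | 75% |

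A separate question is whether an event is never reported at all, with probability (1 - p × c)^n. Take p = 5% and c = 100%, 60% and 30%, again as assumptions:

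- n = 80: 0.95^80 = 1.7%, 0.97^80 = 9%, 0.985^80 = 30%.
- n = 110, relevant to scan and food reactions: 0.4%, 3.5% and 19%.

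**The case against.** The strongest reply is proportionality. No drug is tested, Sections 6.1 and 6.3 describe minimal risk, AEs are not an endpoint, and Section 5.6 plans no AE analysis. The main expected harm of the abstinence challenge, withdrawal, is measured repeatedly. Severe events are escalated under 7.2.1, food allergies are reconfirmed before food is given, and participants have a squeeze ball in the scanner. At the last visit they are told to report later events they believe related. Table 2 is also not exhaustive: the hunger rating is required but has no row. All of this stands, and it limits the importance of the point. It does not supply a general question, because the visit lists lack one as well, and escalation acts only on events already known.

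A reader might infer more than the documents support:

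- *That the frequency example in 7.3.1 cannot work.* It is one item in general IRB reporting text, and it covers greater severity as well as greater frequency. Under-capture lowers sensitivity. In the illustration it nearly removes the signal only when about half the events are missed and the expected rate came from solicited data. The absence of any stated expected rate is a separate difficulty, which asking a question would not cure.
- *That there is no valid denominator.* The enrolled or exposed participants are the denominator; the numerator is what may be incomplete.
- *That nothing is solicited.* The MNWS, PANAS and emotional query are.
- *That 6.1 and 9.3.1 contradict 7.2.1.* Querying emotional reactions supplements self-report, and the regular time points describe monitoring by the team. The wording is loose rather than clearly contradictory. Nor does the zero grade prove that participants are asked, since the same grade is a field on the AE and SAE records.

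**Conclusion.** The point holds as a cheap improvement. Spontaneous self-report is the only stated AE/SAE collection method, and no general question is scheduled at ten smoker visits, six non-smoker visits or the 1-month follow-up. This is a stated, weaker method and more than a missing detail. Under-capture of non-serious events is likely, most plainly for illness, injury, scan-related effects, food reactions and anything arising in days 5-28.

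The size of the loss is not known. The tables in the check rest on assumed expected rates, a doubling of risk, a single capture fraction for all events, and 80 completing smokers; the AE reporting period covers more people than that. They support the statement that frequency signals are weakened, and no more. The efficacy and mechanistic analyses are not affected.

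**What to change.** In Section 7.2.1, add one scripted, non-leading open question about any health problem or change since the last contact. Ask it in identical words of smokers and non-smokers at each in-person visit from Baseline to the last scan, and of smokers at the 1-month follow-up. Add a row to Table 2. Log elicited and volunteered events separately, so that the change in method can be seen in the counts.

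State when the SEC form is used and whether MNWS data enter the AE log. Align Sections 6.1, 7.2.1, 7.2.2 and 9.3.1 with this, including the section number cited in 9.3.1 and what its regular time points are.

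The cost is about a minute at contacts already planned, one line on a case report form, protocol wording, and more minor AEs to log. The change improves capture; it does not by itself supply an expected rate against which frequency could be judged.
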